6.4.3. Nurse diary

Local treatment data at each day will be analysed as recorded in the Study nurse diary.

- Treatment planned (yes/no)
- Complete re-epithelialization of the wound (yes/no)
- Appearance of the secondary dressing BEFORE the dressing removal
 - Normal
 - Saturated
 - Bloody
 - Leakage of exudate
- Appearance of wound
 - Maceration
 - Exudation
 - Foul-smelling odor
 - Irritation/deterioration of PPL
- Local treatment
 - Cleansing of wound
 - Care of PPL
- Application of dressing
 - Moistening of dressing before application
 - Difficulty in applying
 - Problem with conformability
 - Number of dressings used
- Secondary dressing
 - Compresses / gauze
 - Foam
 - Absorbing dressing pad
 - Fixation
 - Superabsorber

- Hydrocolloid
- Gel
- Film
- Other
- Application of venous compression
- Comments

6.4.4. Medical history

Medical history data will be used as recorded in the eCRF.

In addition, the following variable will be computed:

• At least one medical history.

6.4.5. Prior and concomitant therapies

The prior and concomitant therapies will be coded with WHO-DD version SEP 2013 C Version.

The following prior/concomitant treatments will be analysed:

- All prior treatments and care recorded in the CRF ("Prior treatment and care (excluding wound dressings)" form at inclusion).
- Concomitant treatments and care recorded in the CRF. Concomitant therapies are recorded in the "Main on-going general treatment (oral and/or systemic)" form at inclusion and "change in main treatment (oral/systemic)" form at each follow-up visit.

7. DATA ANALYSIS CONSIDERATIONS

7.1. Statistical software

The statistical analysis will be performed using SAS® software v9.4.

7.2. Type I error, handling of multiplicity issues and alpha adjustment procedures

The type I error rate is set to to $\alpha = 0.05$ (two-sided).

However, no formal comparison (i.e. implying a statistical test) is planned.

No multiplicity issue is foreseen; consequently, no procedure for alpha adjustment are planned.

7.3. Site effect and pooling of sites

No site effect will be included into the model, as the site size is expected to be small.

7.4. Descriptive analyses of quantitative and qualitative variables

Quantitative variables will be described by: N (number of patients with non-missing data), mean, standard deviation (SD), minimum, maximum, median, first quartile (Q1) and third quartile (Q3). 95% CIs (binomial) for the means will be presented if they are relevant to the analysis.

Categorical variables will be described by frequency and percentage (over non-missing data) of patients in each category with the 95% CIs. Percentages will be expressed with one decimal place.

7.5. Definition of baseline, time-windows and analysis periods

Baseline:

Baseline is defined as data recorded at the inclusion visit.

Analysis periods: not applicable.

Time-windows: not applicable.

7.6. Handling of missing data and outliers

No missing data will be imputed. AEs with missing relationship, missing seriousness, and/or missing severity will be considered as related to study drug, serious, and severe for the analysis, respectively.

8. PLANNED STATISTICAL ANALYSES

All analyses will be performed on the TS and the PPS.

8.1. Disposition of patients

The following will be provided:

- Number of included patients
- Number of treated patients (i.e. TS)
- Among treated patients, number and percentage of patients who withdraw from the study at Day 56, number and percentage of patients who withdraw from the study before Day 56 and reasons for withdrawal

In addition, the following data will be provided:

- Date of first patient in (i.e. first visit performed)
- Date of last patient out (i.e. last visit performed)

Study duration (days) = date of last patient last visit - date of first patient first visit The template in section 11.4 will be used.

8.2. Protocol deviations

Protocol deviations will be reviewed during the final data review meeting (prior to database lock). The scientific committee will adjudicate them, i.e. decide which deviations are major and should lead to exclusion from the PP set. Decisions from the scientific committee will be documented in the data review minutes.

The following potential major protocol deviations will be reviewed (but not limited to):

- Inclusion criteria not met and/or exclusion criteria met
- Attestation from investigator not available
- Date of inclusion anterior to date of attestation
- Patients who stop Suprasorb® C for reason other than healing of wound
- Withdrawal from the study for reason other than healing of wound
- Missing duration of treatment exposure
- Missing pictures of wound (i.e. "Two pictures of wound after cleansing with saline solution" not ticked "Yes" (i.e. ticked "No" or missing) at Day 28 or Day 56 if the wound is not healed yet.
- Any intermediate therapy (e.g. using different wound dressing) within the treatment period of Suprasorb® C prior to the beginning of granulation
- Missing healing date.

Patients with at least one major protocol deviation will be excluded from the Per Protocol Set.

8.3. Analysis sets

Frequency and percentage of patients included in each analysis set defined in Section 5.1 will be provided.

8.4. Demographic data and baseline characteristics, including medical history and therapies

8.4.1. Demographic data and baseline characteristics

Descriptive analyses will be provided on the TS population using templates available in section 11.1 and 11.2.

8.4.2. Medical history

Descriptive analyses will be provided on the TS population using the template available in section 11.2.

8.4.3. Prior/concomitant treatments

Descriptive analyses of prior treatments and care (excluding wound dressings) will be provided on the TS population using the template available in section 11.2.

Concomitant therapies will be analyzed by WHO-DD preferred name and ATC3 at each visit and overall. The ATC3 will be sorted alphabetically, and WHO-DD preferred names will be sorted by descending frequency (within ATC3, on « total » column) using the template in section 11.3. Treatments recorded in the CRF at D26 and D56 with "Treatment was" variable ticked "stopped" will not be presented in this analysis. Those treatments will only be listed.

8.5. Analysis of the primary endpoint

Reduction of wound area:

A descriptive analysis will be provided overall, on the Treated Set using the template provided in section 11.1.

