Relative change in wound area from baseline to W8 ≤ -15% (yes/no):

This endpoint will be derived as follows:

- Yes, if relative change in wound area from baseline to $W8 \le -15\%$.
- No, if relative change in wound area from baseline to W8 > -15%.

Shift from the healing phase to the granulation phase:

The parameter "shift of phase" will be analysed by Lohmann & Rauscher. However, to compute the combined primary endpoint, the following endpoints will be computed:

Relative change in granulation from baseline to W8 (%) = 100 x (granulation at W8-W0) / W0.

This endpoint will be derived as follows:

- Yes, if relative change from baseline in granulation to W8 > 50%.
- No, if relative change from baseline in granulation to W8 ≤ 50%.

Note:

Granulation (%) of the wound area has been measured by an independent expert using photos. Granulation data of each patient at each visit will be sent by Lohmann & Rauscher to RCTs. RCTs will import the granulation data into the SAS database. Please refer to the Data Transfer Specifications for further details.

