11.1. Table template for numerical data

	Total
	N=XXX
Label of variable (unit)	
Non-missing	XXX
Mean (sd)	XXX(XXX)
Median	XXX
Q1;Q3	XXX; XXX
Min;max	XXX; XXX
Missing	XXX
Etc	

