11.2. Table template for categorical data

	Total
	N=XXX
Label of variable	
Modality 1 [n (%)]	XXX (XXX.X)
Modality 2 [n (%)]	XXX (XXX.X)
Missing [n (%)]	
Non-missing [n (%)]	
Etc.	

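### SAP section 8.5 schedules only a numerical summary of wound-area reduction, so the combined yes/no primary endpoint that the SAP derives has no planned result

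*SAP*

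**What the plan says.** The derivations that stand directly before SAP section 6.2 define two dichotomous variables at week 8. The first is headed "Relative change in wound area from baseline to W8 ≤ -15% (yes/no". The second applies a threshold to the relative change in granulation: "Yes, if relative change from baseline in granulation to W8 > 50" (per cent). Between the two, the SAP leaves the shift-of-phase parameter to the sponsor and then continues: "However, to compute the combined primary endpoint, the following endpoints will be computed".

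Section 8.5 has a single item, "Reduction of wound area", and one instruction for it: "A descriptive analysis will be provided overall, on the Treated Set using the template provided in section 11.1". That template is titled "11.1. Table template for numerical data". A yes/no variable belongs in the next one, "11.2. Table template for categorical data".

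Three other sections bear on the point. Section 8 opens with "All analyses will be performed on the TS and the PPS". Section 7.4 says that categorical variables are described by frequency and percentage over non-missing data, with 95% CIs. Section 7.6 rules out imputation.

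**The concern.** The SAP sets two thresholds in order to build a primary endpoint, and its primary analysis then uses neither. A reader of the resulting report would see the centre and spread of the wound-area change, but not how many patients met the criterion that the plan calls primary. Section 7.2 plans no formal test, so the proportion and its confidence interval would be the whole primary result. If the plan schedules no such output, any responder rate reported later depends on choices made outside it: which variable, which joining rule, which patients in the denominator.

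**Working it through.** The plan gives no figure for this endpoint, so there is none to reproduce. The check compares what is derived with what is scheduled.

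1. **Derived.** Component A is a relative area change to week 8 of -15% or lower. Component B is a relative granulation change to week 8 above 50%. A combination of the two is announced. That makes three yes/no variables. The rule joining A and B is not in the text available for review.

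2. **Scheduled in 8.5.** One item, wound-area reduction, in template 11.1. The template's rows are non-missing count, mean (SD), median, quartiles, minimum and maximum, and missing count. None of them can hold a responder count or percentage.

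3. **Scheduled elsewhere in section 8.**
   - 8.1 to 8.4 cover disposition, deviations, analysis sets and baseline. Granulation is mentioned in 8.2, but only within a potential protocol deviation.
   - 8.6 covers adverse events, duration of use and the endpoints of a section 6.3.12 that does not appear in the SAP. All of this falls under secondary endpoints.
   - 8.7 covers safety.
   - 8.8 covers the other endpoints. The closest is 8.8.2, whose variables (listed in 6.4.2.2) include the absolute area change in cm² and colour segmentation in per cent. Neither threshold is applied there.
   - Result: none of the three yes/no variables has a scheduled output.

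4. **Is the choice of template just shorthand?** Elsewhere the SAP cites 11.2 when the output is categorical: 8.4.2 and 8.8.8 cite it alone, and 8.4.1 and 8.8.1 to 8.8.7 cite it together with 11.1. Section 8.5 cites 11.1 alone.

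5. **Can the combined result be recovered indirectly?** The 8.5 output holds no granulation data, so it cannot. Even if both component rates were known, they would only bound the combined rate. Write a and b for the component rates:
   - both required: from max(0, a + b - 1) to min(a, b)
   - either sufficient: from max(a, b) to min(1, a + b)

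   The rates below are assumed, because the SAP gives none.
   - a = 60%, b = 50%. Both: max(0, 0.60 + 0.50 - 1) = 10% up to 50%. Either: 60% up to min(1, 1.10) = 100%.
   - a = 70%, b = 40%. Both: max(0, 0.70 + 0.40 - 1) = 10% up to 40%. Either: 70% up to min(1, 1.10) = 100%.

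   The combination therefore has to be tabulated from patient-level data.

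6. **Analysis set.** The opening of section 8 requires both the Treated Set (TS) and the Per Protocol Set (PPS). Sections 8.4 to 8.8 name only the Treated Set. The mismatch runs through most of section 8 and is not particular to 8.5.

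7. **Missing components.** With no imputation and percentages over non-missing data, the SAP does not say how to class a patient with one component missing. The answer depends on the joining rule. If both are required, one observed ‘no’ already settles the outcome. If either suffices, one observed ‘yes’ does.

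**The case against.** The strongest objection is relevance. Section 4 of the SAP ties it to the Suprasorb C protocol version 4.0. The supplied protocol randomises Lomatuell Pro against UrgoTul, and its primary endpoint is VAS pain below 30 mm at V2, tested for non-inferiority with a 10% margin. Repairing 8.5 changes no result of that trial. This stands and limits the reach of the point, but the contradiction inside the SAP remains.

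A second objection is that section 7.4 already gives categorical variables a default format. It does, so what is missing is a line scheduling the output and a template reference. But a format rule does not commit the plan to reporting any particular endpoint.

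Four stronger readings are tempting and not supported:

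- *The endpoint requires both criteria.* The visible text names the components and the word combined, but no joining rule. Text just before the derivations was removed before review, so the rule may well be in the SAP. The gap in section 8 is the same under either rule.
- *Granulation is left to the sponsor, outside the plan.* Only the shift-of-phase parameter is. The SAP has the granulation data imported into the SAS database and gives the formula and cut-off itself.
- *Section 8.5 drops the PPS.* It names the Treated Set without excluding the other, and the same wording recurs across section 8. This is a general inconsistency to reconcile.
- *The responder rate can be approximated from the mean and SD by assuming normality.* The SAP gives neither value. Relative area change also cannot fall below -100%, so a normal curve with a wide spread would put patients where none can be.

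**Conclusion.** The point holds as an internal contradiction of the SAP. It announces a combined yes/no primary endpoint and derives both components, and section 8 schedules no output for the combination or for either component. The size is the absence of a primary result: none of three yes/no variables is reported. No numerical bias can be attached to this.

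The conclusion rests on the visible text of section 8, from which nothing was removed between its opening and 8.8.8. It does not depend on the joining rule. The version history records an update of the primary endpoint analysis at version 1.1, which would fit the derivations and 8.5 having fallen out of step, but the documents do not say so.

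This should be corrected in that SAP. It is separate from, and smaller than, the fact that the SAP belongs to a different study from the supplied protocol.

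**What to change.** In section 8.5:

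- Name the combined yes/no variable as the primary endpoint and state its joining rule, taken from the primary-endpoint definition in section 6.
- Report n, % and an exact (Clopper-Pearson) 95% CI for the combination and for each component, using template 11.2. As printed, that template has no row for the interval, so add one.
- Keep the numerical description of area change (template 11.1) as supportive.
- State how a patient with one or both components missing is classed, and give the denominator.
- Reconcile the TS-and-PPS rule that opens section 8 with the Treated Set wording in its subsections, at least for the primary endpoint.

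The cost is a few lines of SAP text and one table per analysis set. The component variables are already derived, so no new data are needed. The change repairs the Suprasorb C plan only. The Lomatuell Pro versus UrgoTul protocol still needs an SAP of its own.

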8.6. Analysis of the secondary endpoints

Frequency and severity of adverse events as well as incidence and side effects in the group of allergic disorders, pain and maceration:

An analysis of AEs will be provided overall, on the TS using the template provided in section 11.5.

All AEs and known risks and side effects will be analyzed as number of events and number and percentage of patients who experienced at least one event.

Known risk and side effects:

AEs related to the known risks and side effects described in section 6.3.1 will be described using the template provided in **Erreur! Source du renvoi introuvable.**

Duration of Suprasorb® C use for wound treatment:

A descriptive analysis will be provided overall, on the Treated Set using the template provided in section 11.1.

A descriptive analysis of the endpoints defined in section 6.3.12 will be provided overall, on the TS using the template provided in section 11.1 and 11.2.

Individual data listings will be provided on the TS.

8.7. Safety analysis

All safety analyses will be performed on the Treated Set.

8.7.1. Adverse events

Overall summary table:

For all AE categories defined in Section 6.3.1, the number of patients who experienced at least one AE of the corresponding category will be provided overall, on the TS, using the template provided in section 11.5.

All AEs will be listed.

All SAEs will be listed.

Analysis by SOC and PTs:

For all AE categories defined in Section 6.3.1, a descriptive analysis by SOC and PT will be provided on the TS, overall. Tables will summarize the total number of events and the number and percentage of patients experiencing the event. The SOC will be sorted alphabetically, and PT will be sorted by descending frequency (within SOC, on « total » column) according to the MedDRA classification (System Organ Class and Preferred Term).

The template provided in section 11.6 will be used.

8.8. Other endpoints

All the following endpoints will be provided on the Treated Set.

8.8.1. Assessment since the last visit

A descriptive analysis will be provided at day 28 and day 56 using the template provided in in section 11.1 and 11.2.

8.8.2. Characteristics of target ulcer

A descriptive analysis will be provided at day 28 and day 56 using the template provided in section 11.1 and 11.2.

8.8.3. Removal of primary Suprasorb® C

A descriptive analysis will be provided at day 28 and day 56 using the template provided in section 11.1 and 11.2.

8.8.4. Local treatment of target ulcer

A descriptive analysis will be provided at day 28 and day 56 using the template provided in section 11.1 and 11.2.

Listing will be provided for text free variables.

8.8.5. Overall assessment of efficacy of study dressing

A descriptive analysis will be provided at day 28 and day 56 using the template provided in section 11.1 and 11.2.

8.8.6. Quality of life

A descriptive analysis will be provided at day 28 and day 56 using the template provided in section 11.1 and 11.2

8.8.7. Overall quality of life at each visit

A descriptive analysis will be provided at day 28 and day 56 using the template provided in section 11.1 and 11.2.

8.8.8. Nurse diary

A descriptive analysis will be provided using the template provided in section 11.2. Listing will be provided for text free variables

9. CHANGES IN THE STATISTICAL METHODS FROM THOSE STATED IN THE PROTOCOL

This SAP is based on protocol version 4.0, CRF version 6.0, Nurse diary version 5.0 and planimetry forms dated 09FEB2018 and 06APR2018.

The intention to treat set was renamed as the Treated Set to be more coherent with the definition, stated in the protocol.

10. QUALITY CONTROL

A self-validation will be performed by the statistician in charge of the analysis as follows: each derived variable will be validated exhaustively (i.e. on all patients) whenever possible. Exhaustive controls can be performed using either contingency tables (i.e. displaying all qualitative variables and minimum/maximum values of quantitative variables involved in the derivation rules) or individual data listings that are considered as not too large (i.e. no more than 50 rows). An exhaustive control is considered possible when the corresponding output contains up to 50 rows. For validation outputs considered as too large (i.e. more than 50 rows), the validation can be performed on a minimum of 10% patients randomly drawn. If the validation output is still too large (i.e. more than 50 rows), the validation will be performed on a subset of 50 rows (minimum).

Validation outputs will be reviewed by a third party (i.e. head of biostatistics or another statistician).

11. TEMPLATES

The following templates will be used.

11.1. Table template for numerical data

	Total
	N=XXX
Label of variable (unit)	
Non-missing	XXX
Mean (sd)	XXX(XXX)
Median	XXX
Q1;Q3	XXX; XXX
Min;max	XXX; XXX
Missing	XXX
Etc	

11.2. Table template for categorical data

	Total
	N=XXX
Label of variable	
Modality 1 [n (%)]	XXX (XXX.X)
Modality 2 [n (%)]	XXX (XXX.X)
Missing [n (%)]	
Non-missing [n (%)]	
Etc.	

11.3. Table template for treatment data

	Total N=XXX		
ATC3/ Pharmaceutical substance(s)	Nb TRT	Nb pat	% pat
Any treatments	XX	XX	XX.X
ATC3 A	XX	XX	XX.X
Pharmaceutical substance 1	XX	XX	XX.X
Pharmaceutical substance 2	XX	XX	XX.X
ATC3 B	XX	XX	XX.X
Pharmaceutical substance 1	XX	XX	XX.X
Etc.	XX	XX	XX.X

11.4. Table template for the disposition of patients

	Total N=XXX
Included [n]	XXX
Treated [n]	XXX
Study withdrawal at Day 56 [n (%)]	XXX (XX.X)
Study withdrawal before Day 56 [n (%)]	XXX (XX.X)
Reason(s) for withdrawal [n]	XXX
	XXX
	XXX

11.5. Table template for the overall summary of AEs

	Total N=XXX
All adverse events (AE)	xxx (xx%)
Serious adverse event (SAE)	xxx (xx%)
Related AE with the study drug according to the investigator	xxx (xx%)
Related AE with the study procedure according to the investigator	xxx (xx%)
AE leading to discontinuation of the study drug	xxx (xx%)
Mild severity AE	xxx (xx%)
Moderate severity AE	xxx (xx%)
Severe severity AE	xxx (xx%)

